3.1. Inclusion Criteria

1. Men and women ≥ 18 years
2. Eastern Cooperative Oncology Group (ECOG) performance status of 0–1 (Appendix I).
3. Symptomatic MM (as defined by revised IMWG criteria) with measurable disease, defined here as having at least one of the following:
 - Serum monoclonal protein ≥ 0.5 g/dL
 - ≥ 200 mg of monoclonal protein in the urine on 24 hour electrophoresis

- Serum immunoglobulin free light chain: involved FLC ≥ 10 mg/dL (≥ 100 mg/L) AND abnormal serum immunoglobulin kappa to lambda free light chain ratio.
- 4. At least 1 prior therapy with demonstrated disease progression following the most recent line of treatment.
- 5. Progression of disease within 60 days of completion of last therapeutic regimen or the failure to achieve minimal response while on last treatment (according to IMWG).
 - Patients should not have progressed on lenalidomide at a dose of more than 10 mg.
- 6. No prior treatment with ibrutinib or any other protein kinase inhibitory drug or drug targeting the BCR signal transduction pathway.
- 7. Patients with prior daratumumab and allogeneic stem cell transplant are included.
- 8. PT/INR $<1.5 \times$ ULN and PTT (aPTT) $<1.5 \times$ ULN, except if on anticoagulation for medical reasons in which case INR should be ≤ 3
- 9. Adequate hematologic function independent of transfusion and growth factor support for at least 7 days prior to registration, with the exception of pegylated G-CSF (pegfilgrastim) and darbopoeitin which require at least 14 days prior to screen and enrollment defined as:
 - Absolute neutrophil count (ANC) $\geq 1000/\text{mm}^3$ independent of growth factor support.
 - Transfusion independent platelet counts $\geq 75,000/\text{mm}^3$ (or $\geq 50,000/\text{mm}^3$ if bone marrow involvement is $\geq 50\%$).
 - Hemoglobin level ≥ 8 g/dL, independent of transfusion support.
- 10. Biochemical values must be within the following limits within 7 days prior to registration
 - Alanine aminotransferase (ALT) and aspartate aminotransferase (AST) $\leq 2.5 \times$ upper limit of normal (ULN).
 - Total bilirubin $\leq 1.5 \times$ ULN (unless bilirubin rise is due to Gilbert's syndrome or of non-hepatic origin).

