13.4. Measurement of Effect

Patients enrolled onto this trial must have measurable disease defined as disease that can be measured either by serum or urinary evaluation of the monoclonal component or by serum assay of FLC and is defined by at least one of the following three measurements:

- Serum M-protein > (0.5 g/dl) g/dl
- Urine M-protein > 200 mg/24 h
- Serum FLC assay: Involved FLC level > 10 mg/dl (> 100 mg/l) provided serum FLC ratio is abnormal.

The disease response will be assessed using criteria based on the International Working Group Uniform Response Criteria in Section 15.3.1. If the only measurable parameter is serum immunoglobulins free light chain (FLC), the participant will be followed by FreeLite™ Disease Response Criteria provided in Section 15.3.2.

The same method of assessment and technique should be used for disease measurement

throughout the study. Disease response should be confirmed by two consecutive assessments at a minimum of 6 weeks apart.

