13.6. Response Criteria

13.6.1 International Myeloma Working Group Response Criteria

Table 17

Response	IMWG criteria
sCR	CR as defined below plus normal FLC ratio and absence of clonal cells in bone marrow by immunohistochemistry or 2 – 4 color flow cytometry
CR	Negative immunofixation on the serum and urine and disappearance of any soft tissue plasmacytomas and < 5% plasma cells in bone marrow. In patients with only FLC disease, a normal FLC ratio of 0.26–1.65 is required.
VGPR	Serum and urine M-protein detectable by immunofixation but not on electrophoresis or ≥ 90% reduction in serum M-protein plus urine M-protein level < 100 mg/24 h In patients with only FLC disease, >90% decrease in the difference between involved and uninvolved FLC levels is required.
PR	≥ 50% reduction of serum M-protein and reduction in 24 hours urinary M-protein by ≥90% or to < 200 mg/24 h If the serum and urine M-protein are unmeasurable, a ≥ 50% decrease in the difference between involved and uninvolved FLC levels is required in place of the M-protein criteria
Stable disease	Not meeting criteria for CR, VGPR, PR, or progressive disease

Progressive disease	
Increase of $\geq 25\%$ from lowest response value in any one or more of the following:
 
Serum M-component and/or (the absolute increase must be $\geq 0.5 \text{ g/dL}$) Urine M-component and/or (the absolute increase must be $\geq 200 \text{ mg/24 h}$) Only in patients without measurable serum and urine M-protein levels; the difference between involved and uninvolved FLC levels. The absolute increase must be $> 10 \text{ mg/dL}$
 
Definite development of new bone lesions or soft tissue plasmacytomas or definite increase in the size of existing bone lesions or soft tissue plasmacytomas Development of hypercalcaemia (corrected serum calcium $> 11.5 \text{ mg/dL}$ or 2.65 mmol/L) that can be attributed solely to the plasma cell proliferative disorder

---------------------	--

Additional response criteria for specific disease states

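### Read as printed, Table 17 gives a patient with urine-only measurable disease and no serum M-protein no route to PR, and lets PR turn on an unmeasurable serum trace in others

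*Combined protocol and SAP*

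**What the plan says.** **Entry (3.1, item 3).** A patient needs "measurable disease, defined here as having at least one of the following", and one of the three listed markers is "≥ 200 mg of monoclonal protein in the urine on 24 hour electrophoresis". The other two are serum M-protein of at least 0.5 g/dL, and involved FLC of at least 10 mg/dL with an abnormal ratio.

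**PR (13.6.1, Table 17).** The requirement is "≥ 50% reduction of serum M-protein and reduction in 24 hours urinary M-protein by ≥90% or to < 200 mg/24 h". The one substitute in that row is "If the serum and urine M-protein are unmeasurable, a ≥ 50% decrease in the difference between involved and uninvolved FLC levels is required".

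**VGPR (Table 17).** There are two alternatives: "Serum and urine M-protein detectable by immunofixation but not on electrophoresis or ≥ 90% reduction in serum M-protein plus urine M-protein level" below 100 mg/24 h. A separate line covers FLC-only patients: "In patients with only FLC disease, >90% decrease in the difference between involved and uninvolved FLC levels is required".

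**Other rows of Table 17.** CR needs negative immunofixation in serum and urine, together with the plasmacytoma and marrow conditions, but no percentage fall. Progression can be called on any single component, urine included. Whatever meets none of CR, VGPR, PR or progression is stable disease.

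**Routing (13.4).** "If the only measurable parameter is serum immunoglobulins free light chain (FLC), the participant will be followed by FreeLite" criteria, which are Table 18.

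**Use (14.3.2 and the secondary endpoint statement after it).** ORR counts sCR, CR, VGPR and PR among patients who began treatment, with a 90% binomial interval. Section 14.3.2 names it the primary endpoint of the expansion portion, while 2.4.1 lists it as secondary. Number and duration of responses by dose level use the same categories.

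**The concern.** Eligibility accepts any one marker, but the PR row asks for a serum fall and a urine condition together, whichever marker made the patient eligible. The urine condition has an absolute alternative (below 200 mg/24 h), which a serum-only patient meets automatically. The serum condition has no such alternative, so the table works for serum-only disease and not for urine-only disease. Table 17 writes FLC-only rules for CR, VGPR, PR and progression, and writes none for urine-only disease. The same urine marker can therefore establish progression but cannot by itself establish PR.

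At stake are the ORR, the count of responses by dose level, and duration of response, which for such a patient could not start before CR. Two assessors could also score the same record differently and each defend the result.

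**Working it through.** The plan gives no figure tied to this rule, so there is none to reproduce. The check applies the printed rules to example records. Inputs are the limits in 3.1, Table 17 and 14.3.2; the patient values are illustrative. The urine end value of 80 mg/24 h is chosen so that VGPR's urine limit of below 100 is met and only the serum wording is being tested.

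**Literal scoring, with no serum M-protein counted as no reduction**

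| Case | Serum M-protein | Urine M-protein (mg/24 h) | PR | VGPR | Scored |
|---|---|---|---|---|---|
| a | absent, immunofixation negative | 1,000 to 80 (92% fall) | no | no | stable disease |
| b | as a | 1,000 to positive on immunofixation only | no | no | stable disease |
| c | as a | 1,000 to immunofixation negative | no | no | CR, if its other conditions hold |
| d | immunofixation positive, no spike | 1,000 to positive on immunofixation only | no | yes, first alternative | VGPR |
| e | 0.3 to 0.1 g/dL (67% fall) | 1,000 to 80 | yes | no | PR |
| f | 0.3 to 0.2 g/dL (33% fall) | 1,000 to 80 | no | no | stable disease |
| g | 2.0 to 0.8 g/dL (60% fall) | 0 throughout | yes | no | PR |

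- Cases a and b fail PR on serum alone. The FLC substitute is closed because urine is measurable, and Table 18 is closed because FLC is not the sole measurable marker.
- Case b fails the first VGPR alternative because, as printed, it asks for serum and urine both to be detectable by immunofixation.
- Cases e and f have the same urine response. They differ by 0.1 g/dL in a serum component below the 0.5 g/dL entry limit. The PR boundary there is 0.3 × 0.5 = 0.15 g/dL.
- Case g confirms that serum-only disease is scored normally.

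**Alternative reading.** If 0 to 0 is taken as meeting a percentage fall, cases a and b meet PR and the second VGPR alternative. The same record is then stable disease or VGPR, depending on a convention the plan does not state.

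**Effect of one misclassified responder on ORR** (1/n)

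- Expansion cohorts in 14.1: 1/10 = 10 points; 1/7 = 14.3 points; 1/4 = 25 points.
- Pooled over the planned 19 to 25 patients: 1/19 = 5.3 points; 1/25 = 4.0 points.

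Exact (Clopper-Pearson) 90% intervals at n = 10, taking 6 true responders as an assumption:

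- none misclassified, 6/10 = 60% (30.4% to 85.0%)
- one misclassified, 5/10 = 50% (22.2% to 77.8%)
- two misclassified, 4/10 = 40% (15.0% to 69.6%)

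**Would dropping the serum condition be enough?** Entry is possible at 200 mg/24 h. A fall to 199 is (200 − 199)/200 = 0.5% and would meet the below-200 limb of PR. A fall to 99 is (200 − 99)/200 = 50.5% and would meet VGPR's below-100 limit. The printed absolute urine cut-offs do not work alone.

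**The case against.** The strongest reply is that this is an ambiguity and not a bar. Table 17 does not say that an absent serum component counts as failed, and a sensible assessor would treat it as not applicable. Section 13.4 says the criteria are based on the International Working Group criteria, which may deal with single-component disease; that cannot be checked from these documents. The reply shows that the intended rule may be reasonable. It does not supply the rule, and where a small serum component exists (cases e and f) the condition clearly applies and gives an arbitrary answer.

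Four stronger readings are tempting but not supported.

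- A reader might infer that every PR needs a serum fall. It does not: the FLC substitute and Table 18 need none.
- A reader might infer that urine-eligible patients can never reach VGPR or count in ORR. VGPR's first alternative is open when serum is positive on immunofixation (case d), and CR and sCR remain open.
- A reader might take 13.4 as stating that response is judged on whichever marker is measurable. It only defines measurable disease and routes FLC-only patients.
- A reader might multiply an assumed urine-only share by the response rates in Table 1 to get an overall ORR loss. The documents give no such share. Table 1 comes from lenalidomide with high-dose dexamethasone after 1 to 3 prior therapies, whereas 3.1 requires progression within 60 days of the last regimen or failure to reach minimal response on it.

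It is also fair to say that the ORR interval is descriptive, with no threshold or decision attached, that it is wide at n = 10, and that dose decisions rest on DLTs. That limits the consequence but leaves the rule in need of correction.

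**Conclusion.** The point holds in a bounded form. Applied as printed, Table 17 gives no PR route to a urine-only patient without serum M-protein, and no VGPR route short of CR if serum immunofixation is also negative. For a urine-eligible patient with serum M-protein below 0.5 g/dL, it makes PR depend on change in a component the protocol does not regard as measurable. Responders lost this way are scored as stable disease and remain in the ORR denominator.

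The size is per patient: 10, 14.3 or 25 points of ORR at n = 10, 7 or 4. The total effect cannot be estimated, because the number of urine-only patients is not given; with none enrolled it is zero. The no-route conclusion rests on reading an absent serum component as not meeting a percentage reduction, and on reading VGPR's first alternative as requiring both serum and urine to be positive on immunofixation. The problem with small serum components needs neither assumption. The rule should be settled before responses are scored, since ORR is named as the expansion portion's primary endpoint and cohorts are very small.

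**What to change.** In 13.6.1, with a cross-reference in 14.3.2, state that:

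1. Serum and urine reduction conditions apply only to components measurable at baseline, using the limits in 3.1.
2. A component not measurable at baseline has only to avoid meeting its own progression criterion.
3. Urine-only patients have an explicit PR and VGPR rule that includes a percentage fall in urine. For PR, one option is the 90% limb already printed, with the below-200 mg/24 h limb reported as a sensitivity analysis. VGPR likewise needs a percentage fall alongside its absolute limit. The sponsor should confirm the exact wording.

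The cost is a few sentences. No new data are needed: 13.5 already calls for serum and 24-hour urine. Under the present schedule (Table 15, footnote i) urine is collected every 3 months after screening, so urine-only responses would be dated and confirmed at those visits.

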2.4. Endpoints

2.4.1 Primary and Secondary

Primary:

1. Maximum tolerated dose (MTD): The maximum tolerated dose (MTD) is defined as the highest dose level among those under consideration where at most 1 of 6 patients develops a dose limiting toxicity and 2 or more of the 3-6 patients treated at the next higher dose level develop a dose limiting toxicity.
2. Safety profile: The maximum grade of each type of toxicity will be recorded for each patient. For each toxicity reported by dose level, the percentage of patients developing any degree of that toxicity as well as the percentage of patients developing a severe degree (Grade 3 or higher) due to treatment will be determined.

Secondary:

1. Progression free survival (PFS) defined as the time from study entry to the documentation of disease progression using IMWG criteria or death due to any cause.
2. Overall survival (OS) is defined as time from registration to death due to any cause.
3. Overall Response rate(ORR)
4. Duration of response, defined as the time from documented response to disease progression among those patients whose disease meets the IMWG criteria for disease response.
5. Safety Profile: CTCAE v5.0 will be used to grade and assign attribution to each adverse event reported.

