2.4.2 Correlative

1. Immunologic studies: bone marrow aspirate and peripheral blood samples will be collected from patients for immunome studies. See Protocol Section 13 for more information.

3. Patient Selection / Population

19-25 patients (9-18 dose escalation; 4-10 dose expansion) with symptomatic multiple myeloma (as defined by IMWG criteria) will be enrolled across multiple investigational sites in the United States. Screening labs must be performed within 7 days prior to registration. Complete body CT scan if clinically indicated at screening must be performed within 14 days prior to registration.

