8.3. Criteria for Discontinuation of Protocol treatment

Patients are continued on treatment until any of the criteria for discontinuation of protocol therapy is met, which includes:

- Tumor progression
- Request by the patient to withdraw
- Unacceptable adverse events
- Treatment delay of >4weeks
- Intercurrent illness which would, in the judgment of the investigator, affect assessments of clinical status to a significant degree or require discontinuation of drug

Administration of non-protocol anti-tumor drug during the trial. Patients who discontinue treatment for any of the above reasons will go to survival follow-up where late toxicities and clinical outcome information will be collected every 6 months for a maximum of 2 years post registration. Once a patient has entered the survival follow-up phase of the trial, his/her therapy is at the discretion of the treating physician.

9. Study Assessments and Procedures

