9.1.5 Follow-up for Other Malignancies

Occurrences of any new malignant tumors including solid tumors, skin malignancies and hematologic malignancies will be reported throughout study participation, including duration of study treatment and during any protocol specified follow-up periods.

Table 15 **Schedule of Assessment**

Treatment Day → Assessments and Procedures ↓	≤ 14 days prior to registration	Day 1 (all cycles)	Day 15 ± 2 days (all cycles)	End of Cycle 1	End of Cycle 3	End of Cycle 6	At end of treatment or treatment discontinuation
History and exam, weight ^a	X	X	X				X
Height	X						
ECOG Performance Status	X	X	X				X
Adverse event assessment	X	X	X				X
Concomitant Medications	X						X
Hematology group: WBC, ANC, ALC, Hgb, and PLT ^b	X	X	X				X
Chemistry group SGOT AST, total bili, Alk Phos, Creatinine, potassium, calcium, magnesium, phosphorus, sodium, albumin), blood glucose ^b	X	X	X				X
TSH, Free T4 ^{cc}	X						
LDH, Uric Acid ^b	X	X	X				X
Serum pregnancy test ^d	X						
Complete body CT	X	X ^e				X ^e	X ^e
Bone Marrow Biopsy ^f	X			X			
Mandatory blood specimens ^g	X	X ^g		X ^g	X ^g	X ^g	
ECG ^h	X						X

Treatment Day → Assessments and Procedures ↓	≤ 14 days prior to registration	Day 1 (all cycles)	Day 15 ± 2 days (all cycles)	End of Cycle 1	End of Cycle 3	End of Cycle 6	At end of treatment or treatment discontinuation
Serum Immunoglobulins, monoclonal protein and free light chain; beta 2 microglobulin ⁱ	X						X

- a. History, exam, and weigh will be done on day 1 of subsequent cycles after cycle 2
- b. Labs will be done weekly for the first 2 cycles, then on day 1 of subsequent cycles
- c. TSH and Free T4 at screening and every 2 cycles
- d. To be performed within 7 days of receiving drug.
- e. If clinically indicated for those with extramedullary disease indicated on baseline CT at completion of cycle 6 (cycle 6 day 28 ±3 days) or to confirm CR
- f. 2 tubes of 5 ml each of bone marrow aspirates in green tube (2) to be collected pre-treatment (prior to start of cycle 1) and at end of cycle 1 (prior to start of cycle 2).
- g. 15 ml peripheral blood to be collected prior to start of treatment and at end of cycles 1, 3, and 6 for the immunome correlate
- h. ECG should be performed within 14 days prior to registration and end of treatment, and as needed during the course of the study.

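### The calcium limit for progressive disease in Table 17 is given as 11.5 mg/dL or 2.65 mmol/L, which are different levels, and nothing says which governs

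*Combined protocol and SAP*

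**What the plan says.** Table 17 in Section 13.6.1 gives the IMWG response criteria. One item under progressive disease is "Development of hypercalcaemia (corrected serum calcium" greater than 11.5 mg/dL or 2.65 mmol/L), with the condition "that can be attributed solely to the plasma cell proliferative disorder". The other routes in the same cell are rises in serum M-component, urine M-component or the free light chain (FLC) difference, and new or enlarging bone lesions or plasmacytomas.

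This is the only calcium limit in the document. Table 18 (Section 13.6.2), to which Section 13.4 directs patients measurable by FLC alone, has no calcium item.

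The criterion is used in three places:
- **PFS.** Section 2.4.1: "Progression free survival (PFS) defined as the time from study entry to the documentation of disease progression using IMWG criteria", or death. Section 14.3 estimates it by Kaplan-Meier.
- **Duration of response.** Under Sections 2.4.1 and 14.3, progression ends it.
- **Treatment.** Section 8.3: "Patients are continued on treatment until any of the criteria for discontinuation of protocol therapy is met", and tumor progression is the first criterion listed.

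Calcium and albumin are both in the scheduled chemistry group of Table 15 ("Creatinine, potassium, calcium, magnesium, phosphorus, sodium, albumin), blood glucose"). Footnote b of that table asks for labs weekly in the first two cycles and then on day 1 of each cycle. Section 3 states that patients "will be enrolled across multiple investigational sites in the United States".

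**The concern.** A limit written in two units should be one limit stated twice. Here the second figure is well below the first, so there are two limits in one sentence and the text ranks neither above the other. A patient whose corrected calcium lies between them, with myeloma judged to be the only cause, can be called progressed or not progressed by two people who both follow Table 17 correctly.

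For that patient, the choice decides whether and when a PFS event is recorded, whether and when a response ends, and whether the progression rule stops treatment. These are individual outcomes in a small, descriptive study.

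**Working it through.** **Inputs.** From Table 17: limits of 11.5 mg/dL and 2.65 mmol/L. From outside the documents: the molar mass M of calcium, 40.08 g/mol, a physical constant (a rounded 40.0 was also tried).

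**Formula.** mmol/L = mg/dL × 10 / M, and mg/dL = mmol/L × M / 10.

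**Attempt to reproduce the plan's pair.**
- 11.5 × 10 / 40.08 = 2.869, so 11.5 mg/dL is 2.87 mmol/L, not 2.65. With M = 40.0 it is 2.875.
- 2.65 × 40.08 / 10 = 10.62, so 2.65 mmol/L is 10.6 mg/dL, not 11.5. With M = 40.0 it is 10.60.

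The pair does not reproduce in either direction.

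**Size of the gap.** 11.5 − 10.62 = 0.88 mg/dL, or 2.87 − 2.65 = 0.22 mmol/L. As a ratio, 2.869 / 2.65 = 1.083, about 8%.

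**Could rounding or another unit explain it?**
- For the two figures to be equal, M would have to be 11.5 × 10 / 2.65 = 43.4 g/mol.
- If 2.65 were meant as mEq/L (valence 2), it would be 2.65 × 40.08 / 20 = 5.3 mg/dL, which is further away.
- Other dual-unit limits in the protocol agree exactly or closely. FLC of 10 mg/dL is 100 mg/L (Section 3.1), and albumin of 3.5 g/dL is 35 g/L (Appendix III). In the same appendix, bilirubin of 2 mg/dL is 2 × 10 / 584.66 × 1000 = 34.2 µmol/L against 34 stated, and 3 mg/dL is 51.3 against 50 stated, under 3% apart (584.66 g/mol is assumed). The calcium gap is larger than any of these.

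**Effect on classification** (each value assumed to meet the attribution condition):

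| Corrected calcium, mg/dL | mmol/L | Above 11.5 mg/dL? | Above 2.65 mmol/L? |
|---|---|---|---|
| 10.5 | 2.62 | no | no |
| 10.7 | 2.67 | no | yes |
| 11.0 | 2.745 | no | yes |
| 11.4 | 2.844 | no | yes |
| 11.6 | 2.89 | yes | yes |

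The two limits disagree for values above about 10.62 and up to 11.5 mg/dL, and nowhere else.

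**When disagreement changes an outcome.** All of the following must hold: the patient is assessed by Table 17 rather than Table 18; the corrected calcium falls in the band; the rise is attributed only to the plasma cell disorder; and no other Table 17 criterion has already established progression. If another criterion is met later, the date of progression moves. If none is met, event status itself depends on the figure used.

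**The case against.** The arithmetic is not in dispute. The case on the other side is that it will seldom matter.

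- **Units in use.** All sites are in the United States, the mg/dL figure comes first, and the protocol's other myeloma measures are in conventional units. If laboratories report calcium in mg/dL, most readers will apply 11.5 and treat 2.65 as a faulty equivalent. This is likely, but it is an assumption: no section names a governing unit, and any mg/dL result can be converted and compared with 2.65.
- **The conjunction.** A reader might infer that the word joining the two figures makes the lower one sufficient by itself. The text does not establish that. On that reading 11.5 would be redundant, and two units joined in this way normally express one limit. What stands is that the sentence does not say which figure is the limit.
- **Attribution and other routes.** A laboratory value alone does not make progression. The investigator must judge the cause, and calcium is one route among several. That calcium is measured regularly does not mean it will regularly trigger a call. This stands in full.
- **FLC-only patients.** They are followed by Table 18, so the conflict should not reach them. This also stands.
- **Endpoints.** The MTD does not use the limit, and the expansion response rate counts sCR, CR, VGPR and PR. The effect is confined to secondary time-to-event summaries and to individual treatment stops.

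These points limit how often the conflict matters. They do not remove it.

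**Conclusion.** The concern holds in a limited form. Table 17 states one progression limit as two different calcium levels, 0.88 mg/dL (about 8%) apart, and nothing in the document reconciles them. A corrected calcium above about 10.6 and up to 11.5 mg/dL, attributed only to the plasma cell disorder, is progression under one figure and not under the other. Where no other criterion has already been met, that patient's PFS event status or date, end of response and progression-based stop of treatment depend on the figure used.

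The conversion rests only on the molar mass of calcium. The view that few patients will be affected rests on mg/dL reporting at United States sites, which the documents do not state. They also give no basis for estimating how many patients would fall in the band.

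Two larger claims are tempting and are not supported. A reader might divide one reclassified patient by 4 to 10 expansion patients and infer a shift of 10 to 25 percentage points in a progression proportion. The plan specifies no such proportion: PFS is a Kaplan-Meier estimate, and duration of response is tabulated by dose level. A reader might also infer that an electronic check or central derivation could be programmed on the wrong figure, but the documents describe neither for progression.

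The documents do not show which figure was intended, and this review does not choose between them.

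**What to change.** The sponsor should reconcile the two values in Table 17 and state one governing limit with its correct conversion. The matched pairs are 11.5 mg/dL with 2.87 mmol/L, or 10.6 mg/dL with 2.65 mmol/L. The choice belongs to the sponsor. The single limit should then apply to all progression calls under Table 17 and to the derivation of PFS and duration of response.

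The cost is one corrected figure in one table cell. No assessment, sample or data item is added.
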